### 4.2 Secondary Hypotheses

The secondary hypotheses are:

1. Compared to baseline, treatment with IFN- $\gamma$ 1b will result in:
  - a. Decreased tibial volumetric bone mineral density (**vBMD**) and estimated bone strength measured by peripheral quantitative computed tomography (**pQCT**);
  - b. Decreased total body and lumbar spine areal BMD (**aBMD**) by dual-energy x-ray absorptiometry (**DXA**);
  - c. Increased levels of markers of bone remodeling (see Table 1);
  - d. Increased osteoclast activity by *in vitro* testing;
  - e. Increased white blood cell (**WBC**) and platelet counts in patients that have lower than expected blood counts at baseline.
  - f. Increased height standard deviation score (**SDS**) for participants <18 years with open growth plates;
  - g. Decreased inflammation measured by erythrocyte sedimentation rate (**ESR**);

[figure not shown]
- h. Decreased pain score (based on prior 4 weeks);
  - i. Increased physical function score (based on prior 4 weeks); and
2. Compared to the 12 months prior to study entry (based on medical record review or subject recollection), treatment with IFN- $\gamma$ 1b over 12 months will result in:
  - a. Decreased number of hospitalizations for infection;
  - b. Decreased number of days treated with antibiotics;
  - c. Beneficial change in WBC and platelet counts in patients who have lower than expected blood counts at baseline;
  - d. Beneficial change in ESR;
  - e. Increased height SDS for participants  $<18$  years with open growth plates; and
3. Patients will not develop neutralizing antibodies.

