## 5.2 Anticipated Duration of the Clinical Investigation

Each subject will be enrolled in the study for 12 months. It is expected that 15 patients will be screened over 18 months to enroll 10 participants, with the final subject completing study participation 2.5 years after study initiation. The final study report will be completed approximately 3 years after study initiation. If the study is terminated prior to completion, a closeout report will be filed with the Institutional Review Board (IRB) within 3 months of study termination.

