#### **5.4.8 Study subject Exit/Discontinuation Criteria**

National Cancer Institute (NCI) Common Terminology Criteria for Adverse Events (CTCAE), Version 4 will be used to define an Adverse Event (AE). The CTCAE Grades 1 through 5 with unique clinical descriptions of severity for each AE will be used and defined as follows:

Grade 1 Mild; asymptomatic or mild symptoms; clinical or diagnostic observations only; intervention not indicated.

Grade 2 Moderate; minimal, local or noninvasive intervention indicated; limiting age-appropriate instrumental Activities of Daily Living (ADL)\*.

Grade 3 Severe or medically significant but not immediately life-threatening; hospitalization or prolongation of hospitalization indicated; disabling; limiting self care ADL\*\*.

Grade 4 Life-threatening consequences; urgent intervention indicated.

Grade 5 Death related to AE.

A Semi-colon indicates 'or' within the description of the grade.

\*Instrumental ADL refer to preparing meals, shopping for groceries or clothes, using the telephone, managing money, etc.

\*\*Self care ADL refer to bathing, dressing and undressing, feeding self, using the toilet, taking medications, and not bedridden.

Subjects will discontinue participation in study for any unexplained CTCAE Grade 3 or higher that is not reasonably related to the underlying disease process or treatments. In addition, subjects will discontinue study participation if any of the following conditions exist:

1. Subject voluntarily withdraws from the study.
2. Subject's death.
3. Subject completes the protocol.
4. Pregnancy.

5. Subject acquires any of the listed exclusion criteria.
6. Subject is non-compliant with the protocol. For example, missing the Month 3 visit (no visit by 120 days after beginning therapy).
7. Subject's well-being, in the opinion of the Investigator would be compromised by continuation in the study.
8. Subject contracts an intercurrent illness that requires treatment not consistent with the protocol requirements.

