#### **6.8 Subject Withdrawal**

Subjects will be encouraged to complete the study; however, they may voluntarily withdraw at any time. If a subject is withdrawn prior to study completion, attempts will be made to schedule and conduct an Early Termination visit for medical assessment. If a subject cannot be contacted after 5 telephone calls and 3 letters, they will be considered lost to follow-up.

Subjects who discontinue study medication (e.g., due to non-compliance, side effects, etc.) will be asked to remain in the study for follow-up per the study schedule to preserve the ability to perform a

safety analysis. If a subject or their legal guardian (as applicable) withdraws consent to participate in the study, attempts will be made to obtain permission to record survival and adverse event (malignancy, hospitalization for infection) data at the 12-month study point.

As long as the link between the sample ID code and the subject name is maintained by the clinical study site, it will be possible for subjects to ask that their samples be withdrawn. However, we anticipate this link will be destroyed at some point in the future, after which withdrawal of samples will not be possible. In addition, once DNA samples have been provided to collaborators, we cannot guarantee that all samples will be able to be tracked down.

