## 7.2 Statistical Methods

### 7.2.1 Sample size Determination

This is a pilot study to obtain data for a larger, definitive clinical trial. The sample size of 10 was determined based on feasibility estimates including potential screening failures

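### Hypotheses 2a and 2b compare raw infection counts with a full prior year, with no denominator or rule for subjects observed for less than 12 months

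*Combined protocol and SAP*

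**What the plan says.** **Endpoints.** The second group of secondary hypotheses in section 4.2 opens with its comparator, "Compared to the 12 months prior to study entry (based on medical record review or subject recollection", and sets 12 months of treatment against it. Hypothesis 2a is "Decreased number of hospitalizations for infection" and 2b is "Decreased number of days treated with antibiotics". Both are numbers, and neither has a time denominator.

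**Follow-up.** Section 5.2 says "Each subject will be enrolled in the study for 12 months". Section 5.4.8 provides for earlier exit: "Subjects will discontinue participation in study for any unexplained CTCAE Grade 3 or higher", limited to events not reasonably attributable to the disease or its treatments. It also lists pregnancy, voluntary withdrawal, death, acquiring an exclusion criterion, non-compliance (the example is no Month 3 visit by day 120) and certain intercurrent illnesses. Section 6.3.1 withdraws a subject who cannot attend Month 3. Section 8.4.2 allows the whole study to be stopped, and a single Grade 4 event is one possible reason.

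**Data after exit.** Section 6.8 asks subjects who stop study drug to stay on the visit schedule, for the sake of the safety analysis. After withdrawal of consent, "attempts will be made to obtain permission to record survival and adverse event (malignancy, hospitalization for infection) data at the 12-month study point". Antibiotic days are not part of that request.

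**Analysis.** Section 7.2.2 does not name infection outcomes among the tested endpoints. Section 7.1 defines a treatment-compliant and a safety population and assigns neither to this comparison. On size, section 7.2.1 says "The sample size of 10 was determined based on feasibility estimates including potential screening failures"; it makes no allowance for dropout.

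**Collection.** The infection item looks back three months (6.3.5.4) and is asked on study at months 3, 6 and 12, not at month 9 (Table 1, Appendix B).

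**The concern.** Every subject brings a complete prior year, while the treated year can be cut short. A difference in raw counts therefore mixes any treatment effect with the length of observation, and truncation can act in one direction only.

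Early exit is not remote here. Continued treatment through the year is part of the primary endpoint, and with 10 subjects each exit is 10% of the sample. Because the plan has no rule, someone must decide how to score leavers after the data are in, in an open-label single-arm study. Section 2.3 says encouraging tolerability and efficacy data will be used to raise clinicians' awareness of the treatment, so a spurious fall in infections would carry weight.

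**Working it through.** **The plan's own figure.** N = 10 rests on feasibility, so there is no power calculation to reproduce. The one arithmetic link is in section 5.2, "15 patients will be screened over 18 months to enroll 10 participants": 10/15 = 0.667. That is a screening yield and says nothing about dropout. Exit numbers, exit times and infection rates below are therefore assumptions.

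**Step 1: size of the shortening.** Let k of 10 subjects leave after a fraction t of the year, with the same constant event rate before and during treatment (no drug effect). If partial counts are used as they stand:

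apparent fall in the treated total = 1 − [(10 − k) + k·t]/10 = k(1 − t)/10.

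Day 120 is the cut-off in the 5.4.8 example: t = 120/365.25 = 0.3285. For k = 2, the fall is 2 × 0.6715/10 = 13.4%.

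| Time of exit | t | k = 1 | k = 2 | k = 3 |
|---|---|---|---|---|
| Day 120 | 0.3285 | 6.7% | 13.4% | 20.1% |
| Month 6 | 0.50 | 5% | 10% | 15% |
| Month 9 | 0.75 | 2.5% | 5% | 7.5% |

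A single subject who leaves at day 120 shows an expected fall of 67%.

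**Step 2: effect on a test.** No test is assigned to 2a or 2b, so this is illustrative. Poisson counts were simulated with equal true rates in both periods (n = 10, 100,000 replicates). A two-sided 5% paired t-test, the method named in 7.2.2 for other continuous endpoints, was applied to the raw counts. Sidedness is assumed, because the plan does not state it. The table gives the share of runs falsely favouring the drug (nominal 2.5%).

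| Events per year (assumed) | No exits | 2 exits at day 120 | 3 exits at day 120 |
|---|---|---|---|
| 0.5 | 2.1% | 3.1% | 3.9% |
| 1 | 2.3% | 4.2% | 5.5% |
| 2 | 2.4% | 5.3% | 7.7% |
| 4 | 2.5% | 6.6% | 10.3% |

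**Step 3: the same data with person-time.** The pooled rate ratio is 1.00 in every scenario. An exact conditional test that uses observed time falsely favours the drug in 0.8% to 1.9% of runs.

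**Step 4: what the denominator must be.** Three look-backs of three months, at months 3, 6 and 12, cover 9 of 12 months; months 6 to 9 are not asked about by this item. Dividing a completer's 9 months of ascertained events by 12 gives 9/12 = 0.75, a 25% fall with no drug effect and no dropout. Interval history (6.3.1) and adverse event recording (8.2) might fill the gap, but the plan does not say that they feed this endpoint.

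**Step 5: the withdrawal sections side by side.** Section 5.4.8 ends participation for non-compliance, and 6.3.1 withdraws a subject who cannot attend Month 3. Section 6.8 asks subjects who stop drug, with non-compliance and side effects as examples, to remain on the schedule. Whether such a subject contributes data to month 12 depends on which section is followed.

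**The case against.** The strongest reply is that the plan nowhere says partial counts will enter the comparison. Hypothesis 2 specifies treatment over 12 months, and if leavers are excluded the shortening bias is zero. The study is also a feasibility pilot, and this secondary comparison cannot alter its primary conclusion. All of that stands. It makes the bias a possible consequence of an unfilled gap rather than a certainty, but it does not supply the missing rule.

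A reader might infer three stronger points that the documents do not support.

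- *That dropping leavers also favours the drug.* This needs infection to drive exit. The Grade 3 rule excludes events reasonably related to the disease, and section 8.4.3 lists infection as an expected event of osteopetrosis. The intercurrent-illness rule applies only where treatment is inconsistent with the protocol, and section 5.4.4 permits all therapies other than HCT, so antibiotics would not obviously trigger it. Pregnancy, voluntary withdrawal and a missed visit have no stated link to infection. The direction of selection is unknown.
- *That antibiotic days are lost for everyone who stops early.* Under 6.8, subjects who stop drug are asked to stay on a schedule that collects antibiotic days. The clear loss is after withdrawal of consent, which makes the case stronger for 2b than for 2a.
- *That the distortion is necessarily large.* Exits at month 9 move the total by 2.5% to 7.5%. At 0.5 events per year, two day-120 exits move false favourable results only from 2.1% to 3.1%.

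**Conclusion.** The concern holds as a defect in how 2a and 2b are defined. Both are raw numbers set against a full prior year, early exit is foreseen, and there is no denominator or scoring rule.

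If partial counts are used, the error favours the drug. With one to three exits of 10, the fall is 6.7% to 20.1% at day 120 and 2.5% to 7.5% at month 9. These figures assume no drug effect, a constant rate and exit unrelated to infection; the plan gives no dropout or infection rates. If leavers are dropped, the comparison describes those who stayed, with a bias of unknown direction.

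Section 6.8 reduces the problem if it is followed. It cannot be relied on while it conflicts with 5.4.8 and 6.3.1, and it does not recover antibiotic days after consent is withdrawn. The change is worth making because a person-time rate is cheap and better than the stated count. The primary feasibility objective is not affected.

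**What to change.** 1. **Sections 4.2 and 7.2.2.** Define 2a as infection hospitalizations, and 2b as antibiotic days, per person-month ascertained on study, against the prior-year count divided by 12. Include all treated subjects and name that population.
2. **Method.** Use a within-subject rate comparison. For hospitalizations, a conditional exact test or a Poisson model with a log person-time offset would serve. For antibiotic days, use a method that allows for clustering of days within courses. Add a sensitivity analysis in subjects with the full 12 months.
3. **Denominator.** Use the time actually asked about. Either ask about infections since the last visit, so that months 6 to 9 are covered, or count only the queried months. Dividing the present three-month look-backs by time to last contact would bring in the 25% shortfall shown above.
4. **Early Termination visit.** Record antibiotic days since the last visit and the date of last contact. The plan does not expressly say that this date is captured.
5. **Withdrawal sections.** Reconcile 5.4.8 and 6.3.1 with 6.8, so that it is clear which subjects continue to contribute data.

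**Cost.** A few sentences, one reworded question and two data items at the Early Termination visit. The downside is that a rate assumes roughly constant risk over the year, so a short treated period is taken to represent a full one. The completers' analysis gives a partial check.

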# **7 Data Collection and Analysis**

## **7.1 Subject Population(s) for Analysis**

- Treatment-compliant population: Any subject who received at least 85% of prescribed doses and attended all scheduled study visits.
- Safety population: All subjects who receive any amount of treatment.

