### 7.2.2 Statistical Analysis

Descriptive analyses of baseline characteristics and outcomes will include means and standard deviations for continuous variables and frequencies for categorical variables. Confidence intervals and P-values will be based on a t-distribution. Statistical significance will be considered as  $p < 0.05$ . The primary endpoint and safety analyses will be primarily descriptive reporting the number and percentage of compliance and AEs. The secondary endpoints for hematologic function, immune function, and bone mineral density will be evaluated by paired t-tests or chi-squared to evaluate change from baseline to 12 months. Secondary endpoints related to in vitro osteoclast assays will be descriptive.

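### Secondary hypothesis 3 asserts that neutralizing antibodies will not occur, which at most 10 subjects cannot support, and the only named interval method, the t-distribution, would give 0% to 0% for 0/10

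*Combined protocol and SAP*

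**What the plan says.** Section 4.2 lists, as the third secondary hypothesis, "Patients will not develop neutralizing antibodies". It attaches no incidence threshold, margin or time point.

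On size, section 7.2.1 says "The sample size of 10 was determined based on feasibility estimates including potential screening failures", and section 5.2 agrees: "It is expected that 15 patients will be screened over 18 months to enroll 10 participants". Section 7.2.1 also gives the purpose: "This is a pilot study to obtain data for a larger, definitive clinical trial".

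On analysis, section 7.2.2 says "Confidence intervals and P-values will be based on a t-distribution" and names no other interval method. Of safety it says "The primary endpoint and safety analyses will be primarily descriptive reporting the number and percentage of compliance and AEs", which does not mention antibodies. The widest analysis set is in section 7.1: "Safety population: All subjects who receive any amount of treatment".

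Sampling is planned in some detail. Table 1 and section 6.3.2 schedule anti-drug antibody (ADA) samples at baseline, weeks 3 and 6, months 3, 6 and 12, and after the last dose until values return to baseline. Section 6.2.4 covers serum for both ADA and neutralizing-antibody assays, but describes the shipped aliquots as being for potential analysis and gives no positivity rule.

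**The concern.** A hypothesis of absence can be supported only by seeing no cases, and no cases in a very small sample says little. Nothing in sections 4.2 or 7.2.2 limits how a result of 0/10 may be read. The one interval method on offer would put a zero-width interval around it.

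What is at stake is a secondary safety result in a pilot that is meant to inform a larger trial. If the result is carried forward as a bare zero, or as zero with a 0% to 0% interval, a reader of the report cannot see that incidences of a quarter or more remain compatible with the data.

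**Working it through.** **The plan's own figure.** The sample size of 10 comes with no assumed rate, power or precision, so there is no calculation to reproduce. Sections 5.2 and 7.2.1 agree on the number.

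**Inputs.** n = 10 is the largest possible denominator (sections 5.2, 7.1 and 7.2.1). n = 8 is an assumption, to show the effect of two subjects without an evaluable result. The incidences p = 5%, 10% and 20% are assumptions too, because the documents give no expected or clinically relevant incidence.

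**1. Chance of seeing no cases.** P(0 of n) = (1 − p)^n.

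| Assumed incidence | n = 10 | n = 8 |
|---|---|---|
| 5% | 0.95^10 = 0.599 | 0.663 |
| 10% | 0.90^10 = 0.349 | 0.430 |
| 20% | 0.80^10 = 0.107 | 0.168 |

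Zero cases in 10 is more likely than not only when p is below 1 − 0.5^(1/10) = 6.7%.

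**2. What zero cases excludes.** This step needs no assumed incidence.
- One-sided 95% upper bound: 1 − 0.05^(1/n), which is 25.9% for 0/10 and 31.2% for 0/8.
- Two-sided 95% Clopper-Pearson upper limit: 1 − 0.025^(1/n), which is 30.8% for 0/10 and 36.9% for 0/8.

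**3. What the t-based interval gives.** Score each subject 0 or 1 and use mean ± t × SD/√n, with t = 2.262 on 9 degrees of freedom.
- 0/10: the mean is 0 and the SD is 0, so the interval is 0% to 0%. The exact interval is 0% to 30.8%.
- 1/10: the mean is 0.10, the SD is √(10 × 0.1 × 0.9/9) = 0.316 and the SE is 0.316/√10 = 0.10. The interval is 0.10 ± 0.226, or about −13% to 33%. The exact interval is 0.3% to 44.5%.

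In the first case the t-based interval implies certainty. In the second it includes impossible values and its upper end is about 12 percentage points too low (44.5 − 33).

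**4. Can treatment-emergent status be determined?** Table 1 and section 6.3.2 include a baseline ADA sample. The ADA row of Appendix B, as it reads in the available text, shows none. The table may have been damaged in extraction, so this needs checking against the source. Appendix B also places the post-last-dose columns under a heading that restricts them to ADA-positive subjects, a condition that Table 1 and section 6.3.2 do not state.

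**The case against.** The strongest defence is that this is an openly feasibility-sized pilot. Item 3 is a one-line expectation in the same style as the rest of section 4.2, with no test or decision rule attached. ADA sits under the safety measures in Table 1, and section 7.2.2 makes safety analyses mainly descriptive, so a count out of n is the natural output. Item 3 feeds neither the primary hypothesis nor the stopping reasons in section 8.4.2.

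Much of that stands, and it rules out three stronger readings.
- A reader might infer that the trial would declare absence as proven. The documents contain no rule for doing so; what they lack is any limit on the reading of zero cases.
- A reader might infer that zero cases is likely even at a clinically relevant incidence. The documents define no such incidence. Above 6.7%, at least one case among 10 is the more likely result; at 10% the chance of none is 35%, and at 20% it is 11%.
- A reader might infer from section 2.3 that an immunogenicity claim would be promoted to clinicians. That section speaks of tolerability and efficacy and does not mention antibodies.

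The defence does not cover the interval. The descriptive sentence in section 7.2.2 refers to compliance and adverse events, so antibody reporting is at best implied, and the t-distribution is the only interval method given. The pilot label explains n = 10 but does not make an absolute hypothesis answerable with it.

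**Conclusion.** The point holds as one of wording and analysis method. At most 10 subjects cannot support a hypothesis that neutralizing antibodies do not occur: 0/10 leaves incidences up to 25.9% (one-sided) or 30.8% (two-sided) compatible with the data, and 0/8 leaves up to 31.2% or 36.9%. These limits depend only on n and the confidence level. The probabilities of 60%, 35% and 11% rest on assumed incidences, and the figure of 8 evaluable subjects is also assumed.

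The t-based interval is a concrete defect for this proportion, because it collapses to 0% to 0% in exactly the case the hypothesis anticipates. It would be going too far to conclude that the trial needs more subjects. Excluding even a 10% incidence with a two-sided limit would take 36 subjects, all negative (ln 0.025 / ln 0.90 = 35.01, rounded up), which is not the purpose of a pilot in a disease this rare. The change should be made, but it concerns a secondary endpoint and leaves the design untouched.

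**What to change.** 1. **Section 4.2, item 3.** Replace the hypothesis with an estimation aim: the incidence of treatment-emergent neutralizing antibodies at any post-baseline sample, including the planned samples after the last dose, among Safety-population subjects with at least one evaluable post-baseline neutralizing-antibody result. A cutoff at month 12 would drop post-treatment samples that Table 1 and sections 6.2.4 and 6.3.2 already provide for.
2. **Section 7.2.2.** State that this proportion is reported as x/n with an exact two-sided 95% Clopper-Pearson interval in place of the t-based interval. State also that zero cases is reported with its upper limit for the actual n (30.8% for 0/10, 36.9% for 0/8) and not as absence.
3. **Consistency.** Reconcile the baseline ADA sample between Table 1 and section 6.3.2 on one side and Appendix B on the other, so that treatment-emergent status can be determined. At the same time, settle whether the post-last-dose samples apply to all subjects or only to ADA-positive ones, and say what counts as an evaluable and a positive neutralizing-antibody result, since section 6.2.4 leaves this open.

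The cost is two lines of text plus the reconciliation, with no new subjects or visits. The price is a less favourable stated conclusion: zero cases would be reported with an upper limit near 31% instead of as an absence.
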